3.3.1 General Study Level Definitions

3.3.1.1 Study period definition

Efficacy analyses are based on planned treatment period, unless otherwise specified. Safety analyses are based on-treatment and/or on-study period.

- Planned treatment period: starts on the date of first dose of IP and ends on the date of the Visit 15 (Week 52) visit or earlier study withdrawal date.
- On-treatment period: starts on date of first dose of IP and ends on earliest(date of last dose of IP + 33 days, date of death, date of study withdrawal). The date of study withdrawal is the completion or discontinuation date from the DISPOSITION eCRF page, where any participant status other than "Completed" has been entered.
- On-study period (planned treatment period and follow-up): starts on the date of first dose of IP and ends on the study completion or withdrawal date.

For analysis performed at primary database lock, the planned treatment period is understood to include all data recorded starting on the date of first dose of IP up until the date of the data cut-off for the primary database lock (details regarding the DCO date and data cleaning can be found in Data Cleaning Requirements for Primary Analysis Lock Plan).

3.3.1.2 Baseline definition

In general, the last non-missing measurement on or prior to the date of the first dose of IP is served as the baseline measurement of efficacy analyses. If there is no value at or prior to the date of the first dose of IP, then the baseline value is not imputed and is set to missing.

In general, the last non-missing measurement at or prior to the date and time of the first dose of IP is served as the baseline measurement of safety analyses. If there is no value at or prior to the date and time of the first dose of IP, then the baseline value is not imputed and is set to missing.

Where unscheduled/repeated assessments exist for any participant at a particular visit, there are also considered in the baseline definitions, provided they remain prior to the date of first dose of IP.

The baseline OCS dose is the prescribed OCS doses prior to the date of the first dose of IP and derived following rules described in Section 3.3.

3.3.2 Visit Window

For summaries and/or analyses presented by time points, visit window need to be defined for classifying records. The visit window is derived from the assessment date relative to the reference start date. This approach allows appropriate classification of visits which may

have occurred significantly earlier or later than the protocol assessment schedule, as well as the use of data captured at visits which have no fixed timing, and the handling of data captured at visits for which the database label is incorrect and unresolvable.

Nominal database visit numbers are not used in any summary or analysis by visit. The relative day is defined as (Date of assessment – Date of first dose of IP) + 1.

Data collected at unscheduled or repeated visits are also included in visit windows, and therefore may be included in summaries or analyses by visit. In the case of a missing value at a scheduled visit, which is then followed by a non-missing value at an unscheduled or repeat assessment within the same visit window, the non-missing value at the unscheduled/repeat assessment replace the missing value at the scheduled visit.

If a participant has more than one non-missing value within the same visit window, the following rules apply:

- The non-missing value closest to the target day is selected for analysis at that visit
- If two non-missing values are the same distance from the target day, the earlier of the two values are selected for analysis at that visit
- If two non-missing values are recorded on the same day and have a different assessment time associated with both of them, the value with the earliest assessment time is selected for analysis at that visit.
- If two non-missing values (for continuous variables) are recorded on the same day and have no assessment time associated with at least one of them, or the same assessment time associated with both of them, the average of the two values are selected for analysis at that visit. For categorical variables in this situation, the worst case is used.

If a participant has no value within a particular visit window, then the participant has a missing value at that visit in summaries and analysis.

The same visit window definitions are used regardless of whether the planned treatment period or the on-treatment period is used for analysis. Each data record in the planned treatment period is first identified, and then further flagged as on-treatment if applicable. This flag is used to select all eligible records for subsequent visit windowing, according to whether the derived visits are to be used in a planned treatment period or an on-treatment period analysis. It should be noted that, if treatment was discontinued within a particular visit window, the rules above for handling two values within the same visit window could select a different record according to whether a planned treatment period analysis or an on-treatment period analysis is needed.

Table 3 summarises the visit windows to be used. "4-weekly Visit Window" corresponds to the 4-weekly protocol scheduling for clinic visits, including those variables which are not captured at every clinic visit, unless otherwise stated. Sparse visit windows are defined also for specific parameters not measured every 4 weeks.

The 4-weekly visit window approach is replaced by a weekly based approach for ACQ-6 measured weekly. For Week 1, the window is [2; 11] and then for each week, the window is defined as (Target day for Week X - 3; Target day for Week X + 3), where Target day for Week X = (Week number * 7) + 1. For example: Target day for Week 10 is 71 (i.e., 10*7+1) and the visit window is (68 - 74).

Visit windows presented in Table 3 does not apply for calculation of daily OCS dose at each timepoint. The OCS dose at each visit is based on actual visit dates to account for changes in OCS dose at scheduled visit. The visit window at Week X is calculated as [Visit(X-1) date + 2 days; Visit(X) date + 1 day]. For Week 52, the visit window is [Visit 14 date + 2 days; Visit 15 date].

Table 3. Adjusted analysis Visit Windowing

Visit	Time	Target	4-weekly Visit	Spar	Sparse Visit Window			
	Point	Day	Window	(Sparse CSP sch		edule)		
				AQLQ	SGRQ/ PPOCS/ SNOT-22	AIRQ		
Visit 2	Week 0	1	NA	NA	NA	NA		
Visit 3	Week 4	29	2 - 42	2-56	-	-		
Visit 4	Week 8	57	43 - 70			-		
Visit 5	Week 12	85	71 - 98	-	-	-		
Visit 6	Week 16	113	99 - 126	-	-	-		
Visit 7	Week 20	141	127 - 154	-	-	-		
Visit 8	Week 24	169	155 - 182	-	-	-		
Visit 9	Week 28	197	183 - 210	169-224	169-224	-		
Visit 10	Week 32	225	211 - 238	-	-	-		
Visit 11	Week 36	253	239 - 266	-	-	-		
Visit 12	Week 40	281	267 - 294	-	-	-		
Visit 13	Week 44	309	295 - 322	-	-	-		
Visit 14	Week 48	337	323 - 350	-	-	-		
Visit 15	Week 52	365	351 - 378	337-378	337-378	337-378		
Visit 16	Week 64	449	≥379	-	-	-		

In all cases above, no time points are presented in summary tables or included in statistical analysis which do not correspond to the time points scheduled in the protocol for the variable in question. Listings of data includes all scheduled and unscheduled visits.

3.3.3 Handling of Unscheduled Visits

Data collected at unscheduled or repeat visits are also included in visit windows, and therefore may be included in summaries or analyses by visit. For the analyses displayed according to study visit, please refer to Section 3.3.2 to determine scheduled/unscheduled visit handling.

3.3.4 Multiplicity/Multiple Comparisons

No formal hypothesis tested in this study, and no multiplicity adjustment applied in the statistical analysis.

3.3.5 Handling of Protocol Deviations in Study Analysis

Participants who do not meet eligibility criteria but enrolled is analysed according to FAS as described in Section 3.2. There is no intention to perform a per-protocol analysis in this study. Only important protocol deviations are listed and tabulated in the Clinical Study Report (CSR), and only participants in FAS (not screening failures). Important protocol deviations are a subset of protocol deviations that may significantly impact the completeness, accuracy, and/or reliability of the study data or that may significantly affect a participant's rights, safety, or well-being.

Important protocol deviations are defined prior to first participants enrolled. Participants are not excluded from any analysis sets on the basis of any important protocol deviations. The list of important protocol deviations is documented prior to primary DBL (Week 28) and final DBL and includes but are not limited to the following categories:

- Informed Consent (version, process, signature/date, presence/absence, other)
- Study Conduct/Procedures (inclusion/exclusion criteria, study assessment study restrictions/withdrawal criteria, sample processing/storage, sample shipping, other)
- Investigational Product (supply, dispensing/accountability, handling/storage/retention, dose formulation/dose administration, sample collection, other)
- Safety (recording, reporting/follow-up, other)
- GCP violation

The process for identification and assessment is detailed in a separate Protocol deviation plan.

4 STATISTICAL ANALYSIS

This section provides information on definitions, derivation and analysis/data presentation per domain.

4.1 Study Population

4.1.1 Subject Disposition and Completion Status

4.1.1.1 Definitions and Derivations

Disposition information and completion status are directly obtained from electronic case report form (eCRF). Regions are defined as follows:

- Central/Eastern Europe: Bulgaria, Latvia, and Poland
- Western Europe: Belgium, Germany, France, Spain, and United Kingdom
- South America: Argentina and Mexico
- North America: Puerto Rico and United States of America.

4.1.1.2 Presentation

Participants' disposition is summarised and presented graphically on the All participants analysis set. The number of enrolled participants, number of participants who received IP, did not receive IP (and reasons), completed treatment, discontinued treatment (and reasons), completed 28 weeks of treatment, discontinued treatment at or prior to Week 28 (and reasons), completed study (participants who completed IP and study, and participants who discontinued IP but completed study assessments), withdrew from study (including reasons), and withdrew from study at or prior to Week 28 (including reasons). The number and percentage of participants, who discontinued IP, but remained in the study is presented by option of follow up (i.e., 1: Return for all regular clinic visits and perform all scheduled assessments; 2: Monthly telephone follow-up with eDiary completion; 3: Contact at Week 52).

Participant's disposition variables, except for the completed treatment and completed study, are also presented for the interim analysis. The summary is presented on the All participants analysis set.

The number of subjects who discontinued treatment or withdrew from study due to global/country situation together with reasons is presented based on Full Analysis Set. The number and percentage of participants with at least one missed visit, visits contact mode affected by global/country situation is presented. A listing of all participants impacted by global/country situation is produced with details of changed or missed visits.

Participant recruitment by region, country and centre is summarised based on Full Analysis Set.

4.1.2 Analysis Sets

4.1.2.1 Definitions and Derivations

Definitions of analysis sets are provided in Section 3.2.

4.1.2.2 Presentation

The number and percentages of participants are presented for each analysis set.

4.1.3 Protocol Deviations

4.1.3.1 Definitions and Derivations

The definition of protocol deviations and derivations are described in Section 3.3.5.

4.1.3.2 Presentation

Protocol deviations are summarised using FAS. The number and percentage of participants with at least one important protocol deviation as well as each important protocol deviation is described.

Information of participants with important protocol deviation is also listed.

PDs related to global/country situation are defined in the Protocol Deviation Plan. The IPD related to global/country situation are summarised together with all other Important PDs as described in Section 3.3.5. An additional summary is provided of Important PDs related to global/country situation and Important PDs excluding global/country situation related Important PDs for the FAS. A listing of all global/country situation related protocol deviations (important and non-important PDs) is provided.

4.1.4 Demographics

4.1.4.1 Definitions and Derivations

All demography information can be directly retrieved from the eCRF. Age is directly collected in the eCRF as well as sex, ethnicity and race. In addition, participants are classified based on age group (\geq 18 to <65 years, \geq 65 years).

4.1.4.2 Presentation

Demographics are summarised using frequency counts and percentages (for categorical variables) and n, mean, standard deviation, median, minimum and maximum (for age variable) using the FAS and the currently or historically elevated EOS populations. Demographics are also summarised for the interim analysis on the FAS.

4.1.5 Baseline Characteristics

4.1.5.1 Definitions and Derivations

Various baseline characteristics are summarised in FAS and the currently or historically elevated EOS populations. These include height (cm), weight (kg), BMI (kg/m²) calculated

as weight (kg) divided by (height (m))², BMI categorised ($<25 \text{ kg/m}^2$; 25 to $<30 \text{ kg/m}^2$; $\ge30 \text{ kg/m}^2$), post-BD FEV1 (L), ACQ-6 score, daily OCS dose (mg), daily OCS dose categorised as in Section 4.2.1.7, biomarker levels (FeNO, eosinophils and IgE), biomarker levels categorised as in Section 4.2.1.7, and allergic status defined as follows:

- Baseline (Any) specific IgE status (FEIA): Any FEIA positive, All FEIA negative, Unknown FEIA
 - "Any FEIA positive" requires 1 or more specific IgE panels using fluorescent enzyme immunoassay (FEIA) to be positive. Provided that at least one IgE panel is positive, no further requirement is made for data on all 11 panels to be available.
 - "All FEIA negative" requires all 11 specific IgE panels to be negative.
 - If there are fewer than 11 panels with data available and none of these is positive, then IgE status is considered "Unknown FEIA".
 - Positive is defined as a value >0.35 kU/L.
- Baseline perennial specific IgE status (FEIA): Any perennial FEIA positive, All perennial FEIA negative, Unknown perennial FEIA
 - "Any perennial FEIA positive" requires 1 or more specific IgE (FEIA) panels to be positive. Provided that at least one IgE panel is positive, no further requirement is made for data on all 7 panels to be available.
 - "All perennial FEIA negative" requires all 7 specific IgE panels to be negative.
 - If there are fewer than 7 panels with data available and none of these is positive, then IgE status is considered "Unknown perennial FEIA".
 - Positive is defined as a value ≥ 0.35 kU/L.
 - The 7 panels include: American Cockroach, Cat Dander, D. farina, D. pteronyssinus, Dog Dander, German Cockroach, Mould Mix.
- Baseline specific IgE status (FEIA): Any seasonal FEIA positive, All seasonal FEIA negative, Unknown seasonal FEIA
 - "Any seasonal FEIA positive" requires 1 or more specific IgE (FEIA) panels to be positive. Provided that at least one IgE panel is positive, no further requirement is made for data on all 4 panels to be available.
 - "All seasonal FEIA negative" requires all 4 specific IgE panels to be negative.

- If there are fewer than 4 panels with data available and none of these is positive, then IgE status is considered "Unknown seasonal FEIA".
- Positive is defined as a value \ge 0.35 kU/L.
- The 4 panels include: Grass Mix Pollen, Silver Birch Pollen, Weed Mix Pollen, Japanese Cedar.

4.1.5.2 Presentation

Baseline characteristics are summarised in a similar manner to that described for baseline demographics (see Section 4.1.4.2). Baseline characteristics are also summarised for the interim analysis on the FAS.

4.1.6 Disease Characteristics

4.1.6.1 Definitions and Derivations

Baseline disease characteristics includes the asthma duration, age at onset of asthma, GINA classification (mild, moderate, severe), asthma history characteristics (allergen/aspirin/exercise /other asthma trigger, previous admission to ICU, need of mechanical ventilation). Number of asthma exacerbations in the previous 12 months, number of asthma exacerbations requiring hospitalisations in the previous 12 months, any asthma exacerbation required hospitalisation, asthma exacerbation medications are also described.

 $Age\ at\ onset\ of\ asthma=Asthma\ diagnosis\ year-Year\ of\ birth+1.$

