4.1.6.2 Presentation

Disease characteristics are summarised on the FAS in a similar manner to that described for baseline demographics (see Section 4.1.4.2).

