4.1.7 Medical History and Concomitant Disease

4.1.7.1 Definitions and Derivations

Medical history information can be directly obtained from the eCRF. In case of a partial diagnosis date, if both the month and the year are available then the 1st is imputed for the day. If only the year is available, 1st January is imputed.

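### SAP 4.1.6.1 derives age at onset of asthma as diagnosis year minus birth year plus 1, which is one or two completed years too high for every participant

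*SAP*

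**What the plan says.** SAP section 4.1.6.1 opens its list of variables with "Baseline disease characteristics includes the asthma duration, age at onset of asthma" and gives one formula for the second of these: "Asthma\ diagnosis\ year-Year\ of\ birth+1". It gives no reason for the added 1, no alternative derivation and no rule based on full dates. Section 4.1.6.2 then says "Disease characteristics are summarised on the FAS in a similar manner to that described for baseline demographics (see Section 4.1.4.2". Under section 4.1.4.2 that means n, mean, standard deviation, median, minimum and maximum for a continuous variable.

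Two other places give context. Age at study entry is not derived at all: "Age is directly collected in the eCRF as well as sex, ethnicity and race" (section 4.1.4.1). The SAP also adds 1 in its day counts, for example "The relative day is defined as (Date of assessment – Date of first dose of IP) + 1" (section 3.3.2).

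**The concern.** Adding 1 is right when days are counted inclusively, so that the first day is Day 1. The SAP does this for relative day, exacerbation duration, time to oral corticosteroid reduction and extent of exposure. An age is elapsed time, not an inclusive count, so the term has no place there. It may have been carried over from the day-count formulas, but the SAP does not say.

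At stake is one row of a table describing who was enrolled. Followed as written, the formula shifts the location and range of that row upward. It can never return 0, so a participant diagnosed in the year of birth is reported as aged 1. The report would also show age at entry and age at onset on different conventions, and age at onset would not be comparable with sources that use ordinary age. Age at diagnosis is of some interest to this programme: Protocol section 2.2 mentions it when describing how consistent the exacerbation results of an earlier tezepelumab trial were.

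**Working it through.** The plan states no numerical age at onset, so there is no figure to reproduce. The check is calendar arithmetic on the formula.

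**Inputs**
- D = year of asthma diagnosis, B = year of birth, k = D − B (SAP 4.1.6.1).
- I = 1 if the diagnosis falls before the birthday in year D, otherwise 0.
- Onset is taken to be the time of diagnosis, as the SAP does.
- Assumption, for averages only: birth and diagnosis dates are spread evenly over the calendar year.

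**Against completed years**
- Completed age at diagnosis = k − I, so it is k or k − 1.
- SAP value = k + 1.
- Error = (k + 1) − (k − I) = 1 + I, which is 1 or 2 and never 0. This needs no distributional assumption.

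**Against exact decimal age**
- Exact age lies between k − 1 and k + 1, with mean k under the even-dates assumption.
- Error = (k + 1) − exact age, which lies between 0 and 2 years with mean (k + 1) − k = 1.0.

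**Examples**

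| Born | Diagnosed | SAP value | Completed age | Error |
|---|---|---|---|---|
| 15 Mar 1980 | 1 Sep 2010 | 2010 − 1980 + 1 = 31 | 30 | +1 |
| 15 Sep 1980 | 1 Mar 2010 | 2010 − 1980 + 1 = 31 | 29 | +2 |
| 1 Feb 2000 | 1 Nov 2000 | 2000 − 2000 + 1 = 1 | 0 | +1 |

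**Simulation**

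In 400,000 simulated pairs of birth and diagnosis dates:
- The error in completed years was +1 in 50.2% and +2 in 49.8%, and took no other value. The mean is 1 × 0.502 + 2 × 0.498 ≈ 1.5 years.
- Against exact age the excess ran from 0.001 to 1.997 years, with mean 1.000.

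**The same check without the +1**
- D − B = k, so the error in completed years is k − (k − I) = I: 0 in 50.2% and +1 in 49.8% of the simulated pairs.
- Against exact age the mean error is k − k = 0 under the even-dates assumption.
- Compared with D − B, the SAP formula raises the mean, median, minimum and maximum by exactly 1 and leaves the standard deviation unchanged.

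**The case against.** The strongest points on the other side concern scale, the repair and weight, not the arithmetic.

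- **Scale.** The range of one to two years holds for completed age at diagnosis. On exact age the excess can be anything between 0 and 2 years. Diagnosis also only stands in for onset; if onset came earlier, the true error in age at onset is larger and cannot be found from the documents. This stands as a qualification, and it does not help the formula.
- **The repair is not perfect.** Without the +1, the result is still one completed year too high for about half of participants. This also stands. However, D − B is always within the possible range of completed ages except that it may need rounding down by one, and it is unbiased for exact age under evenly spread dates. The SAP value has neither property.
- **A year-of-life convention may be meant.** Someone aged 30 is in the 31st year of life. The SAP does not say this, and the variable is labelled as an age. Even on that reading k + 1 is right only when the birthday has passed, about half the time.
- **Programme alignment.** The SAP amendment history says that several presentations were set to match other tezepelumab studies. The documents do not show whether this derivation is shared. That is a reason to check before editing, not a defence of the formula.
- **Weight.** Age at onset is not an eligibility criterion, a subgroup in section 4.2.1.7 or a covariate in the repeated-measures models, and it enters no endpoint or safety analysis. Section 4.1.6.2 plans no interim display of it. Section 4.1.6.1 gives no formula for asthma duration, so no carry-over of the error can be claimed. All of this stands and keeps the point minor.

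**Conclusion.** The formula is wrong as written. It gives a value that cannot be a completed age at diagnosis for any participant and overstates that age by exactly 1 or 2 years. This follows from the calendar alone. The averages, about +1.5 against completed years and +1.0 against exact age, rest on evenly spread dates. Everyone in the FAS with both years recorded is affected, always in the same direction, so averaging over participants does not remove the error. The effect is confined to one descriptive baseline row, and no efficacy or safety estimate changes. The point is a low-severity correction.

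**What to change.** In SAP section 4.1.6.1 and the matching program, define age at onset of asthma as the year of asthma diagnosis minus the year of birth, without the added 1. State that it is a calendar-year difference, which can exceed completed age by one year. If full birth and diagnosis dates are collected, deriving completed age from them is exact; the SAP should then say what is done when only a year is known. Section 4.1.7.1 has such a rule for partial diagnosis dates ("If only the year is available, 1st January is imputed"), but it sits under medical history and is not stated to apply here.

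The cost is a one-term edit and a rerun of one table, plus a quick check whether other studies in the programme share the derivation. Design, data collection and sample size are unaffected.
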